### Follow-up after completion of treatment

All patients, provided that they have not withdrawn consent for follow up, should have long-term follow-up of at least 5 years, irrespective of whether they have discontinued trial treatment prematurely. The anticipated follow-up frequency is once every year, unless otherwise clinically indicated. Follow-up after relapse should be according to local policy.

The following information will be collected:

- Local/distant relapse
- Response to other agents used to treat recurrent/progressive tumour
- Toxicity
- Survival
- Important information relevant for the trial (unforeseen circumstance that may have led to changes in interpretation of the results, for instance, cause of death)

## FIGURE 1: FLOWCHART OF ASSESSMENTS

This table provides a summary of the trial-related procedures required; refer also to full text in section 9

YEAR	1						FOLLOW-UP
	S 	B 	2	3	4	5	
Visit							
Timeframe		Day 1	Day 14	4 wks	8 wks	12 wks	16 wks
Medical history	X						
Clinical examination	X	X		X	X	X	X
Events 				X	X	X	X
Adverse Events/SAEs 			X	X	X	X	X
Tumour assessment by calipers	X			X	X	X	X
Tumour assessment by ultrasound	X						X
Routine bloods	X						X
Trans NEO-EXCEL Bloods		X	X				X
Core Biopsy		X	X				
Formalin fixed tumour tissue cut from surgical specimen							X*

FROZEN TISSUE SUB-PROTOCOL Frozen core biopsies** and frozen sample from* surgical specimen		X**	X**				X*	
--	--	-----	-----	--	--	--	----	--

The Trans NEO-EXCEL sub-protocol is applicable to all sites

The frozen tissue sub-protocol will only apply to sites that are participating in frozen tissue collection

If for any reason Trans NEO-EXCEL blood samples cannot be taken always send all pathology samples

### Notes:

Medical history to include clinical examination, height, weight, ECOG status, concomitant medication.

1 - Screening visit

2 - Baseline visit (to take place *up to* 5 days before treatment start)

3 - Breast cancer events and survival (disease progression or recurrence, death with cause)

4 - As described in section 13

\*\*Frozen core biopsies \* From surgical specimen

If patients are withdrawn due to disease progression a core biopsy should be performed prior to initiation of alternative treatment and Trans NEO-EXCEL blood samples should also be taken

Patients should continue to take their trial medication until the day of surgery (patients should not take study medication after requirement of 'nil by mouth' for anaesthetic purposes)

## 10. TRIAL MANAGEMENT / DATA COLLECTION

NEO-EXCEL will be coordinated by the Cancer Research UK Clinical Trials Unit at the University of Birmingham according to the current guidelines for Good Clinical Practice. Participating sites may be monitored by Trials Unit staff to confirm compliance with the protocol and the protection of patients' rights as detailed in the Declaration of Helsinki (Appendix 3).

### 10.1 Trial start-up and core documents

Interested sites should contact the NEO-EXCEL Study Office to obtain information on the core documentation required prior to trial participation. All Principal Investigators taking part in the trial will be asked to sign a Clinical Trial Agreement (which will detail the responsibilities of the participating site) and should provide a current signed and dated *Curriculum Vitae* prior to trial activation.

It is recommended that all clinic and study-related personnel should attend a start-up meeting for training on trial procedures and data collection methods. Staff from sites that have attended the trial launch meeting will not require a start-up visit unless specifically requested by the local Investigator or NEO-EXCEL Study Office.

The Principal Investigator at each site must submit this protocol, any supporting documentation, and any subsequent amendments for Site-Specific Assessment from their Local Research Ethics Committee and, if locally required, Institutional Review Boards. Investigators must acquire ethical approval and R&D/Trust approval before they commence recruitment.

### 10.2 Case Report Forms

The CRFs will contain common information, but this information will be kept to a minimum. The CRFs must be completed and signed/dated by the Investigator or one of their authorised staff members as soon as the required information is available. The completed originals should be sent to the NEO-EXCEL Study Office, with a copy held by the Investigator at site. In all cases it remains the responsibility of the Investigator to ensure that they have been completed correctly and that the data are accurate. Entries should be made in ballpoint pen preferably in black ink and must be legible. Any errors should be crossed out with a single stroke, the correction inserted and the change initialled and dated. If it is not clear why a change has been made, an explanation should be written next to the change. Typing correction fluid should not be used. Data reported on each CRF should be consistent with the source data or the discrepancies should be explained. All sections are to be completed before returning to the NEO-EXCEL Study Office. If information is not known, this must be clearly indicated by entering NK on the form. All missing and ambiguous data will be queried.

Trial CRFs may be amended as appropriate; this will not constitute a protocol amendment. Revised CRFs should be used by all participating sites with immediate effect.

## Case Report Forms will include:

- Eligibility Form
- Randomisation Form
- On-study Form
- On treatment follow-up Forms
- Post-operative Form
- Withdrawal/long-term follow-up Forms
- Relapse/Death Forms
- Adverse Event (AE)/Serious Adverse Event (SAE) Forms

### 10.3 Early withdrawal from trial treatment

Patients should be withdrawn from the trial if there is evidence of disease progression. Patients can also be withdrawn at the discretion of the Investigator or at the patient's own request. *Patients have the right to withdraw from the trial at any time for any reason.* Full details of the reason(s) for withdrawal should be recorded on the CRFs if clinician-initiated, otherwise a simple statement reflecting patient preference will suffice.

Please note that patients who withdraw from trial treatment will not be regarded as having withdrawn consent for ongoing follow-up and data collection unless clearly specified at time of withdrawal, and should therefore be followed-up in accordance with the protocol.

### 10.4 Data monitoring

The Trial Coordinator will be in regular contact with site personnel (by phone/fax/email/letter) to check on progress and answer any queries that they may have. Trial staff will check incoming CRFs for compliance with the protocol, consistent data, missing data and timing. Sites may be barred from further recruitment in the event of serious and persistent non-compliance and/or very poor recruitment.

Monitoring will be done according to the Trials Unit policy and the NEO-EXCEL Monitoring Plan. Investigators will allow the trial monitors access to source documents as requested. If a monitoring visit is required the NEO-EXCEL Study Office will contact the site to arrange a date for the proposed visit. Data to be verified will include:

- Informed Consent
- Eligibility
- Adverse Events
- Outcome

Any major problems identified during monitoring will be reported to the NEO-EXCEL Steering Committee. All records will be maintained in accordance with local regulations and in a manner that ensures security and confidentiality. The completed original CRFs are the sole property of the NEO-EXCEL Steering Committee and should not be made available in any form to third parties (except for authorised representatives of appropriate Health/Regulatory Authorities) without written permission from the NEO-EXCEL Steering Committee.

## **10.5 Closure of trial – end date**

For the purposes of Clinical Trial Authorisation (CTA) under the European Union Directive 2001/20/EC, the study is deemed to have ended 30 days after the last patient receives the last dose of the Investigational Medicinal Product (IMP).

For the purposes of Multicentre Research Ethics Committee approval, the study end date is deemed to be the date of last data capture.

## **10.6 Archiving**

To enable monitoring, peer review and/or audits from Health Authorities, the Investigator must agree to keep records, including the identity of all participating subjects (sufficient information to link records e.g. CRFs and hospital records), all original signed Informed Consent Forms, copies of all CRFs and detailed records of drug disposition.

To comply with international regulations these records should be retained by the Investigator for 15 years, including assessments such as CT scans.

## **10.7 Trial Steering Committee / Trial Management Group**

The Trial Steering Committee will provide the overall supervision for the trial, in particular: trial progress, protocol compliance, patient safety and review of updated information.

The Trial Management Group will be responsible for the clinical set-up, on-going management, promotion of the study, and for the interpretation of the results.

This is a clinician-initiated and clinician-led trial, funded through a project grant from Cancer Research UK, and an educational grant from the pharmaceutical industry. The study has been independently peer reviewed and endorsed by Cancer Research UK Clinical Trials Awards & Advisory Committee (CTAAC), and is part of the National Cancer Research Network (NCRN portfolio).

## **10.8 Independent Data Monitoring Committee**

An Independent Data Monitoring Committee (IDMC) for the trial will be responsible for the regular monitoring of trial data. The Committee will consist of two clinicians not entering patients into the trial and an independent statistician. The IDMC will assess the progress of the trial and give advice on whether the accumulated data from the trial, together with the results from other relevant trials, justifies the continuing recruitment of further patients. The committee will first meet to review data from the first 400 patients randomised (see section 14.4) and then annually thereafter until the trial closes to recruitment. The IDMC may consider discontinuing the trial if the recruitment rate or data quality are unacceptable or if there are cases of excessive toxicity that in the IDMC's opinion jeopardise patient safety. In addition the IDMC may recommend the trial stop early if the interim analyses showed differences between treatment arms that are sufficient to be deemed convincing to the general clinical community. If a decision is made to continue, the IDMC will advise on the frequency of future reviews of the data on the basis of accrual and event rates. The IDMC will make confidential recommendations to the Trial Steering Committee (TSC) as the decision-making Committee for the trial.

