### **APC**

In the Adenoma Prevention with Celecoxib (APC) Trial, celecoxib demonstrated a statistically significant increased cardiovascular risk over placebo. The doses of celecoxib in this trial were 400-800mg per day. These findings were unexpected and not consistent with other reported findings from the PreSAP trial. Patients taking 400 and 800mg of celecoxib daily had an approximately 2.5-fold increase in their risk of experiencing a major fatal or non-fatal cardiovascular event compared to those taking placebo.

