## 8. TREATMENT DETAILS

### 8.1 Trial plan

**Treatment should begin within 5 working days of randomisation. The planned duration of treatment is 16 weeks.**

## **Subjects will be randomised (1:1:1:1) to receive either:**

### **Exemestane + Celecoxib**

Patients will receive exemestane 25mg, one tablet daily and celecoxib 400mg, one capsule twice daily

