### **Letrozole + Celecoxib**

Patients will receive letrozole 2.5mg, one tablet daily and celecoxib 400mg, one capsule twice daily

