### **14.4 Timing of interim and final analyses**

The first interim analysis will be carried out and presented to the Independent Data Monitoring Committee (IDMC) after 400 patients have been recruited into the trial. This analysis will assess recruitment, toxicity, compliance, number of adverse/treatment related events and response. It is anticipated that interim analyses will be carried out and presented to the IDMC annually thereafter. See Section 10.8 for further details. The final analysis and publication of results for all outcomes except time-to-event measures, will be carried out once all randomised patients have completed surgery. The final analyses and publication for time-to-event outcome measures will occur when all randomised patients have a minimum of 2 years follow-up and again at a minimum of 5 years follow-up.

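### The first IDMC review, for safety as well as response, waits for 400 randomised patients with no calendar trigger, so about 200 celecoxib patients are allocated before any scheduled independent comparison by arm

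*Protocol*

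**What the plan says.** Protocol section 10.8 makes the IDMC responsible for monitoring the trial data on a regular basis. It lists grounds on which the committee may consider stopping: excessive toxicity, an unacceptable recruitment rate, unacceptable data quality, or convincing differences between arms. On timing it says "The committee will first meet to review data from the first 400 patients randomised", with annual meetings after that.

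Section 14.4 agrees. Its initial look at the data "will be carried out and presented to the Independent Data Monitoring Committee (IDMC) after 400 patients have been recruited into the trial". It combines safety and efficacy in one look: "This analysis will assess recruitment, toxicity, compliance, number of adverse/treatment related events and response".

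On exposure, section 8.1 says "Subjects will be randomised (1:1:1:1) to receive either" one of four arms. The two celecoxib arms read "Patients will receive exemestane 25mg, one tablet daily and celecoxib 400mg, one capsule twice daily" and "Patients will receive letrozole 2.5mg, one tablet daily and celecoxib 400mg, one capsule twice daily". Planned treatment is 16 weeks, with surgery between 16 and 18 weeks.

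On risk, section 3.5.2 reports that in the APC trial "celecoxib demonstrated a statistically significant increased cardiovascular risk over placebo. The doses of celecoxib in this trial were 400-800mg per day", with a risk of major cardiovascular events about 2.5 times that on placebo. The same section reports no increase in PreSAP at 400 mg daily and none for celecoxib in the preliminary, unadjudicated ADAPT results.

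**The concern.** One patient-count trigger serves two purposes that call for different timing. A first look at response needs a reasonable number of assessed patients. A first look at safety and conduct is most useful early, before a problem has run through much of the trial.

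Two consequences follow from the text.

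- The committee's own grounds for stopping cannot be used in the first 40% of recruitment, because it has not yet met.
- A pure count trigger works backwards for recruitment and data quality. The slower the accrual, the later the committee meets. If accrual stalls below 400, it has no scheduled meeting, although poor recruitment is one of the things it is asked to judge.

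The celecoxib comparison is placebo-controlled, so an excess of events that also occur in the background is hard to recognise case by case. Each can reasonably be called unrelated. Appendix 6 leaves out of the related category any event with only a remote or unlikely link to the product. Such an excess shows up only in a comparison by arm.

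**Working it through.** **Inputs from the protocol.** Total 1000, with 500 celecoxib versus 500 placebo (14.3); first review at 400 (10.8, 14.4); allocation 1:1:1:1 with celecoxib in two arms, 400 mg twice daily, for 16–18 weeks (8.1); risk ratio about 2.5 in APC (3.5.2).

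**Input assumed.** The protocol gives no background cardiovascular event rate. A range of 0.5%, 1% and 2% per year is used.

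**Patients allocated before the first review.**
- The plan's own figure: 1000 × 2/4 = 500 celecoxib patients, as section 14.3 states.
- At the trigger: 400 × 2/4 = 200, and 200/500 = 40%. Daily dose: 2 × 400 = 800 mg.

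**Exposure, if all 200 complete treatment.** 200 × 16/52 = 61.5 and 200 × 18/52 = 69.2 patient-years. Some patients would still be on treatment at the 400th randomisation, and the data cut is not fixed, so exposure in the report could be lower. Further patients may also be randomised before the committee meets.

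**Expected cardiovascular events over 16 weeks.** Placebo = rate × patient-years; celecoxib = 2.5 × placebo; excess = 1.5 × placebo.

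| Assumed rate per year | Placebo (200 patients) | Celecoxib (200 patients) | Excess |
|---|---|---|---|
| 0.5% | 0.005 × 61.5 = 0.31 | 0.77 | 0.46 |
| 1% | 0.01 × 61.5 = 0.62 | 1.54 | 0.92 |
| 2% | 0.02 × 61.5 = 1.23 | 3.08 | 1.85 |

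**The same at an illustrative review of 100 randomised patients.** There would be 50 on celecoxib, giving 50 × 16/52 = 15.4 patient-years. Expected celecoxib events run from 2.5 × 0.005 × 15.4 = 0.19 to 2.5 × 0.02 × 15.4 = 0.77. The Poisson chance of seeing none is exp(−0.19) = 83% to exp(−0.77) = 46%.

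**Timing.** The protocol passages on the IDMC and sample size give no accrual rate. Reaching 400 within 12 months needs 400/12 = 33 patients a month. At half that rate the first review comes at 24 months. With a trigger of 100 patients or 12 months, whichever is earlier, the calendar limb applies once accrual falls below 100/12 = 8.3 a month.

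**What else operates before 400.**
- SAE forms within 24 hours, and assessment of each case by a Clinical Coordinator (13.3).
- Expedited SUSAR reports and annual summaries of serious adverse reactions to the regulator and ethics committee (13.3).
- Unblinding of individual events thought to be related (13.5).
- General oversight of patient safety by the Trial Steering Committee, with no schedule or access to data by arm stated (10.7).

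These judge single events or summarise events already judged related. None is stated to be a comparison between arms.

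**The case against.** The strongest reply is that safety is watched from the first dose and that the cardiovascular evidence is weaker than the APC figure alone suggests. Much of this stands.

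- A reader might infer that nobody sees unblinded data before 400. Section 13.5 does not support that, because the coordinating centre unblinds individual events thought to be related. What is absent is a scheduled independent comparison by arm.
- A reader might also infer that the Steering Committee and Trial Management Group are barred from seeing data by arm. The protocol does not say so.
- A reader might carry the 2.5-fold risk straight over to these 200 patients. That figure comes from one trial with treatment for up to 4 years, against 16–18 weeks here. PreSAP and preliminary ADAPT point the other way, and section 6.2 excludes ischaemic heart disease, cerebrovascular disease, NYHA II–IV failure and uncontrolled hypertension.
- An early look would probably not detect the cardiovascular effect that prompts the worry. The event counts confirm this: under one expected celecoxib event at 100 randomised patients.
- The two sections agree with each other, so the timing is a choice and not a miscalculation. The IDMC may also change how often it reviews the data.

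The last argument has a limit. That power to alter the frequency arises only from the first meeting, and the first meeting is what the count trigger delays. None of the other points supplies a comparison by arm or a meeting date if accrual is slow.

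**Conclusion.** The point holds as a gap in the timing of independent oversight. About 200 of 500 planned celecoxib patients (40%) are allocated, at 800 mg/day, before any scheduled independent comparison by arm, and no review is scheduled if accrual stops short of 400. That sits badly with a committee charged with regular monitoring and allowed to act on toxicity, recruitment and data quality.

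The documents do not support reading this as a large unseen cardiovascular hazard. Under the assumed background rates and the full 2.5-fold ratio, the expected excess among the first 200 celecoxib patients is about 0.5–1.8 events. An earlier review is worth having for gross imbalance, commoner toxicity, compliance and withdrawals, not for a modest cardiovascular effect. The figure of 200 rests only on the stated allocation and trigger. The event counts rest on the assumed rates and on all 200 completing 16 weeks. This is an inexpensive improvement that should be made, not an error that invalidates the design.

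**What to change.** In sections 10.8 and 14.4, separate the safety review from the response review.

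- Add an early closed IDMC review, by arm, of toxicity, SAEs, compliance and withdrawals, without response data. Trigger it by calendar time or a smaller patient count, whichever is earlier. Twelve months from first entry or 100 randomised patients would serve as an example; the exact trigger is for the sponsor and the IDMC to set.
- Keep 400 patients as the first look at response.
- Because section 8.1 withdraws patients whose tumours progress, leave progression withdrawals out of the by-arm table or show them pooled, so that the report carries no response information.

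With no response data shown and no test of the primary endpoint made, the review uses none of the 5% significance level. It draws on adverse event and treatment data already collected and needs no extra patients or assessments. The cost is amendment wording, one extra closed report and one extra meeting of the existing committee.

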## 11. CONCURRENT STUDIES

Patients entering NEO-EXCEL may be considered for entry into additional trials provided compatibility has been agreed by Trial Management Groups or Steering Committees of both studies.

## 12. STUDY DRUG SUPPLIES

Full pharmacy details and guidelines for ordering study drug supplies, and labelling requirements are contained within the NEO-EXCEL Pharmacy File which will be sent to the appointed Pharmacist.

## 13. PHARMACOVIGILANCE

### ADVERSE EVENTS: DEFINITIONS AND REPORTING

The collection and reporting of data on Adverse Events and Serious Adverse Events will be in accordance with EU Directive 2001/20/EC and UK legislation.

#### 13.1 Adverse Event definitions

##### **Adverse Event**

An Adverse Event (AE) is defined as any untoward medical occurrence in a patient or clinical trial subject administered a medicinal product and which does not necessarily have a causal relationship with this treatment.

##### *Comment*

An AE can therefore be any unfavourable and unintended sign (including abnormal laboratory findings), symptom or disease temporally associated with the use of an Investigational Medicinal Product (IMP), whether or not considered related to the IMP.

##### **Adverse Reaction**

An Adverse Reaction (AR) is defined as all untoward and unintended responses to an IMP related to any dose administered.

##### *Comment*

An AE judged by either the reporting Investigator or Sponsor as having causal relationship to the IMP qualifies as an AR. The expression reasonable causal relationship means to convey in general that there is evidence or argument to suggest a causal relationship.

##### **Unexpected Adverse Reaction**

An Unexpected Adverse Reaction (UAR) is defined as an AR, the nature or severity of which is not consistent with the applicable product information (e.g. Summary of Product Characteristics (SmPC)).

##### *Comment*

When the outcome of an AR is not consistent with the applicable product information the AR should be considered unexpected.

Severity: The term severe is often used to describe the intensity (severity) of a specific event. This is not the same as serious, which is based on patients/event outcome or action criteria.

